1. INTRODUCTION

The term insulin sensitivity-insensitivity is referred to for the first time in 1936 by Himsworth, who took a background from redactions dating back to 100-200 BC. of C. Insulin sensitivity is defined as its effectiveness in lowering blood glucose by promoting glucose uptake by muscle and adipose tissue cells, increasing hepatic glycogen production, and reducing hepatic glucose production.^{2,3} Therefore, insulin resistance is a pathophysiological phenomenon in which, for a given concentration of this hormone, an adequate reduction in blood glucose levels is not achieved, which results in the event for which the individual is able to maintain a normal tolerance to glucose over finite periods and comes intolerance carbohydrates and at consequence, the occurrence of various diseases as diabetes mellitus, the arterial hypertension and central obesity.^{4,5}

Early diagnosis of insulin resistance along with timely intervention can prevent the onset of these conditions. He currently has several methods for measuring sensitivity, within which the most accurate and precise, considered the "gold standard" is the clamp to hyperglucemic-hyperinsulinemic. However, they are expensive and time-consuming and personnel-intensive, so they are limited for use in specialized experimental clinical research centers and not as a diagnostic means. This has led to the search and development of indices that allow to quantify insulin sensitivity/resistance, classified according to the data used for the calculation in:⁷

1. Indices calculated using fasting plasma concentrations of insulin, glucose and triglycerides: HOMA-IR (Homeostatic Evaluation Model), Quantitative verification of insulin sensitivity (QUICKI), insulin sensitivity (ISI), Raynaud's, fasting insulin resistance (FIRI), Bennett, triglycerides and glucose (TyG).
2. Indices calculated using plasma insulin and glucose concentrations obtained over 120 min of a standard (75 g glucose) PTOG: Hyperglycemic-hyperinsulinemic clamp (CLAMP), McAuley, Belfiore, Cederholm, Avignon, Stumvoll, Gutt, Matsuda.

Recently, an index based on the oral glucose insulin sensitivity index (OGIS) in combination with anthropometric variables, called PREDIcted M (PREDIM), has been proposed; however, there is no evidence of its validation with respect to the various indices for the evaluation of insulin sensitivity, so the objective of this protocol is compare them with the afore mentioned indices.⁸

2. MATERIALS AND METHODS

2.1 Study desing

An analytical cross-sectional study will be carried out.

2.2 Universe of work

Healthy male and female population, 30 to 60 years old, residents of the Guadalajara metropolitan zone.

2.3 Sample size

The sample size was calculated with the formula for simple correlation in a group ⁹:

$$n = 3 + \frac{K}{C^2}$$

	PREDIcted M (PREDIM)
	Insulin sensitivity
Confidence level	95 %
Statistical power	80 %
K (Z α + Z β)	13.0 ⁹
R	0.692 ⁸
C= 0.5 ln $\frac{1+r}{1-r}$	0.8517
N	20.92
n with 20 % losses	25

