2.6 Study groups and administration of the intervention

- 25 healthy patients will be tested for oral glucose tolerance **test**.

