3. STATISTIC ANALYSIS

Statistical analyses will be performed using SPSS statistical software (version 25). Values will be presented as measures of central tendency and dispersion, mean \pm standard deviation. Nominal variables in numbers and percentages. The Kolmogorov-Smirnov test will be performed to determine if the variables follow a normal distribution. Spearman correlation coefficients will be used to analyze the univariate relationship between index Predicted M (PREDIM) technique with various indices (McAuley, Belfiore, Cederholm, Avignon, Matsuda, Gutt, Stumvoll, HOMA-IR, ISI, Raynaud, QUICKI, FIRI, Bennett and TyG). A *P* value less than 0.05 will be considered significant.

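### The sample-size table states 80% power, but its constant K = 13.0 and its N = 20.92 correspond to 95% power at two-sided 0.05

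*Combined protocol and SAP*

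**What the plan says.** Section 2.3 introduces the calculation thus: "The sample size was calculated with the formula for simple correlation in a group". The formula is n = 3 + K/C², where C is the Fisher transform of the expected correlation. The table gives a confidence level of 95%, an entry of 80% for "Statistical power", K = 13.0 (label beginning "K (Z α + Z β"; value attributed to a cited sampling text), r = 0.692, C = 0.8517, N = 20.92, and 25 after allowing for 20% losses.

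Section 2.6 carries the 25 forward: "25 healthy patients will be tested for oral glucose tolerance".

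Section 3 sets the threshold and the test. Its rule for the threshold is that any P "value less than 0.05 will be considered significant". As to the test, for PREDIM against each comparator, "Spearman correlation coefficients will be used to analyze the univariate relationship". The comparators number 14, listed there as "McAuley, Belfiore, Cederholm, Avignon, Matsuda, Gutt, Stumvoll, HOMA-IR, ISI, Raynaud, QUICKI, FIRI, Bennett and TyG". No sidedness, stricter alpha or multiplicity adjustment is stated.

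**The concern.** K is not a free input. It is fixed by the significance level and the power, both of which the table states. For 95% confidence and 80% power the familiar two-sided value is 7.85, yet the table uses 13.0.

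Section 2.3 is the plan's only justification for enrolling 25 people. If its inputs disagree, a reader cannot tell what power the study was designed for, and a report that repeats 80% power together with N = 20.92 would repeat an incorrect statement. The direction also matters: a K that was too small would leave the study underpowered, while one that is too large means the stated N exceeds what the stated power needs.

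**Working it through.** **Inputs (section 2.3; threshold from section 3).** Alpha 0.05, power 80%, K = 13.0, r = 0.692, C = 0.8517, N = 20.92, 20% losses, 25 enrolled.

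**1. Reproduce the plan's N.** C = 0.5 ln(1.692/0.308) = 0.8518. With the printed C, 3 + 13.0/0.8517² = 20.92. The stated N follows from K = 13.0, so 13.0 is the value that was used and not a misprint.

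**2. Recompute K = (z_α + z_β)².**

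| Alpha | Power | K | N = 3 + K/C² |
|---|---|---|---|
| 0.05 one-sided | 80% | (1.645 + 0.842)² = 6.18 | 11.52 |
| 0.05 two-sided | 80% | (1.960 + 0.842)² = 7.85 | 13.82 |
| 0.05 two-sided | 90% | 10.51 | 17.48 |
| 0.05 two-sided | 95% | (1.960 + 1.645)² = 12.995 | 20.91 |

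Taking the label literally, as an unsquared sum, gives 2.80 (two-sided) or 2.49 (one-sided) at 80% power, which does not yield 13.0 either.

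**3. What K = 13.0 implies.**
- At two-sided 0.05, power = Φ(√13 − 1.960) = 0.950.
- At 80% power, two-sided alpha = 2[1 − Φ(√13 − 0.842)] = 0.0057. The plan states no such alpha.

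**4. Size at the stated 80% power.** N = 13.82, so 14 evaluable. With 20% losses: 14 × 1.2 = 16.8 (17) or 14/0.8 = 17.5 (18).

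For the planned Spearman test, assume a variance factor of 1.06:
- If 0.692 is a Spearman value: 3 + 1.06 × 7.849/0.8518² = 14.47 (15).
- If 0.692 is a Pearson value under bivariate normality, Spearman rho = (6/π) asin(0.692/2) = 0.675, and 3 + 1.06 × 7.849/atanh(0.675)² = 15.39 (16).

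**5. Power with 20 evaluable (25 less 20%) and with all 25, two-sided 0.05.** Fisher z: Φ(C√(n − 3) − 1.960). Spearman: Φ(atanh(rho)√((n − 3)/1.06) − 1.960).

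| Case | n = 20 | n = 25 |
|---|---|---|
| Fisher z, r = 0.692 | 94.0% | 97.9% |
| Spearman, rho = 0.692 | 92.7% | 97.3% |
| Spearman, rho = 0.675 | 90.7% | 96.2% |
| Spearman, rho = 0.5 (illustrative) | 59.5% | 70.6% |
| Fisher z, r = 0.692, assumed Bonferroni 0.05/14 | 72.5% | 86.0% |

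Simulation with 40,000 bivariate-normal samples per case agrees for the three Spearman rows: 92.7% and 97.4%; 90.9% and 96.3%; 60.8% and 71.9%.

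**6. Smallest Spearman rho with 80% power in one unadjusted test.** tanh(2.802√(1.06/(n − 3))) = 0.604 at n = 20 and 0.548 at n = 25.

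**The case against.** The strongest reply is that nothing practical turns on this. The discrepancy is conservative for the calculation the table makes, 25 people are enrolled either way, and no test or endpoint changes. That stands, and it limits the seriousness of the point. It does not make the stated power correct.

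A second reply is that K comes from a cited source not available here, that sidedness is not stated, and that 13.0 also fits one-sided 0.01 with 90% power (13.02). The reason for choosing 13.0 indeed cannot be checked. But that alternative matches neither the stated confidence level nor the stated power, and no citation can make 13.0 the constant for 95% confidence and 80% power.

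Third, relabelling the table as 95% power is exact only for its own formula at N = 21 (95.1%). After 20% losses 25 becomes 20, where Fisher-z power is 94.0%. By the 1.06 formula, 95% Spearman power needs 3 + 1.06 × 12.995/0.8518² = 21.99 (22), or 3 + 1.06 × 12.995/atanh(0.675)² = 23.5 (24) if 0.692 is a Pearson value. This is fair, and is why the achieved power should be stated beside the label.

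Fourth, the rho = 0.5 and Bonferroni figures rest on assumptions that are not in the plan. They are illustrations of where the conservative reading ends and are no part of the contradiction.

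Two other features of the table are separate points: K is labelled as a sum although 13.0 is the squared sum, and 20.92 × 1.2 = 25.1 was rounded down to 25, whereas 20.92/0.8 = 26.15 would round up to 27.

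**Conclusion.** The concern holds. At alpha 0.05, one- or two-sided, 80% power does not give K = 13.0. At two-sided 0.05, K = 13.0 and N = 20.92 carry 95% power, 15 points above the stated figure; equivalently, the stated N is about 7 above the 14 that 80% power needs under the table's own formula. Whether the power entry or K was unintended cannot be told from the documents.

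The study is not underpowered on this ground for a single unadjusted test at r = 0.692. This rests on that correlation being realistic and, for the Spearman figures, on the 1.06 variance factor and on whether 0.692 is a Pearson or a Spearman value. The margin does not carry over to a correlation near 0.5, and with 20 evaluable it would not survive a Bonferroni correction over the 14 comparisons. What needs correcting is the reproducibility of the design statement.

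**What to change.** Keep 25 enrolled and reconcile the section 2.3 table in one of two ways:

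- state 95% power for K = 13.0 and N = 21, making clear that this is the Fisher-z calculation; or
- state K = 7.85 and N = 14 for 80% power (15–16 if sized for the planned Spearman test), and note that 25 exceeds this.

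Then add two sentences:

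- the power of a single test at r = 0.692 with 20–25 evaluable participants: about 94–98% by Fisher's z, or about 91–97% for Spearman, saying whether 0.692 is taken as a Pearson or a Spearman value;
- the smallest Spearman rho detectable with 80% power in a single unadjusted test: about 0.60 at n = 20 and 0.55 at n = 25.

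Optionally, say which measure of insulin sensitivity the 0.692 with PREDIM refers to. The cost is one table edit and two sentences, with no change to enrolment or analysis.

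### The sample-size table is internally inconsistent: K = 13.0 corresponds to 95% power, not the stated 80%, and 25 enrolled covers 16% losses, not 20% (minor correction)

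*Combined protocol and SAP*

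**What the plan says.** Section 2.3 is the only justification of the sample size. It says that "The sample size was calculated with the formula for simple correlation in a group" and gives n = 3 + K/C². The table lists "Confidence level 95" (per cent), "Statistical power 80" (per cent), K = 13.0 taken from reference 9, r = 0.692 taken from reference 8, C = 0.8517 and N = 20.92. The last row, "n with 20 % losses", is 25. Section 2.6 carries that number forward: "25 healthy patients will be tested for oral glucose tolerance".

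Section 3 plans Spearman correlations between PREDIM and each of the other indices, with a P "value less than 0.05 will be considered significant". Neither section says whether the test is one- or two-sided, and Section 2.3 does not say how the 20% was applied.

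**The concern.** Two things in one short table fail a routine check.

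The larger is that K should follow from the confidence level and the power, and 13.0 does not follow from 95% and 80%. A reader cannot tell whether the design target is 80% power, for which the formula asks for about 14 people, or 95% power, for which it asks for 21.

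The smaller is the loss allowance. Losses come out of those enrolled, so a 20% loss has to be covered by dividing by 0.8. The stated 25 looks like a multiplication by 1.2.

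What is at stake is whether the stated power, K and enrolment can be relied on when the size of the study is reported. The ability of the study to detect the assumed correlation is not at stake, as the working shows.

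**Working it through.** **Inputs.** From Section 2.3: r = 0.692, K = 13.0, confidence 95%, power 80%, losses 20%, n = 25. From Section 3: significance threshold 0.05 and Spearman correlation. Two-sided testing is my assumption; the one-sided case is checked below.

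**Reproducing the plan's N.**
- C = 0.5 ln(1.692/0.308) = 0.8518 (the plan prints 0.8517).
- N = 3 + 13.0/0.8518² = 3 + 17.92 = 20.92. This agrees with the plan.

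**K against the stated power.** K is (z for alpha + z for power)².
- Two-sided 5%, 95% power: (1.960 + 1.645)² = 12.99, which is the plan's 13.0.
- Two-sided 5%, 80% power: (1.960 + 0.842)² = 7.85. Then N = 3 + 7.85/0.8518² = 13.8, so 14, or 18 enrolled after dividing by 0.8. Both are Pearson figures.
- One-sided 5%, 80% power: K = 6.18. Read one-sided, K = 13.0 would mean about 97.5% power.

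Neither sidedness makes 13.0 agree with 80%.

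**Loss allowance, if N = 20.92 is kept.**
- 20.92 × 1.2 = 25.10. The plan's 25 is this figure rounded down.
- 25 × 0.8 = 20, below 20.92 (21).
- Losses that 25 can bear while leaving 21: (25 − 21)/25 = 16%.
- 20.92/0.8 = 26.15, so 27; 27 × 0.8 = 21.6. With 26 enrolled, 26 × 0.8 = 20.8, still just under 20.92.

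**Power actually available at r = 0.692, two-sided 5%.** Power = Φ(C × √((n − 3)/f) − 1.960), where f = 1 for Pearson. For Spearman, f is a variance factor that the documents do not give. I assume a range from 1.06 to 1 + r²/2 = 1 + 0.692²/2 = 1.24.

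| Evaluable n | Pearson, f = 1 | Spearman, f = 1.06 | Spearman, f = 1.24 |
|---|---|---|---|
| 14 | 80.7% | 78.4% | 71.8% |
| 20 | 94.0% | 92.7% | 88.4% |
| 21 | 95.1% | 93.9% | 90.1% |
| 25 | 97.9% | 97.3% | 94.8% |

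For example, at n = 20 with f = 1: 0.8518 × √17 = 3.512; 3.512 − 1.960 = 1.552; Φ = 94.0%.

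With 20 evaluable, power exceeds 80% under every factor. With 14 it does so only under the Pearson formula, so 14 (and 18 with losses) should not be read as sizes for the planned Spearman analysis.

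**The case against.** The strongest objection is that nothing follows for the study. The stated target is 80% power, and 20 evaluable participants give well over that. If 80% is the real requirement, the Pearson formula needs 14, and 25 enrolled could lose 11 and still have them. The one-person shortfall exists only if K = 13.0 is retained. This stands, and it is why the loss allowance is a sub-point and the whole matter a minor correction.

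A reader might infer from the loss row that the trial is too small, or that two more people must be enrolled. The documents do not support either inference: against its stated power the study is larger than its formula requires.

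It can also be said that the plan gives no formula for the loss row, so 20% may simply have been added to N. That explains the 25 apart from the rounding: 25.10 rounds up to 26. But the row is labelled as losses, and 20% lost from 25 leaves 20 however the figure was reached.

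The elimination criteria in Section 2.4.3 (nausea, vomiting, faintness, intolerance of the glucose load, withdrawal) make some losses possible. The design is cross-sectional, though, with one test visit after screening, and apart from the 20% allowance itself nothing in the documents suggests that more than 4 of 25 will be lost.

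Finally, K comes from a reference that is not available here. That leaves open which entry is mistaken, but it does not make 13.0 compatible with 80%.

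**Conclusion.** The point holds as a minor correction. The power label and K cannot both be right: K = 13.0 is 95% power at two-sided 5%, against 80% stated. The documents do not settle which entry was intended. Conditional on keeping K = 13.0 and N = 20.92, the enrolment of 25 covers 16% losses rather than 20%, a difference of one evaluable participant (20 against 21) or two enrolled (25 against 27).

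At the planned 20% loss rate, power for r = 0.692 is 94% by the plan's own type of formula and about 88–93% for Spearman. These figures assume a two-sided 5% test of a single correlation, the plan's r, and the assumed range of the Spearman variance factor.

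**What to change.** Keep 25 and restate the table in Section 2.3:

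- Make K and the power label agree. The edit that leaves N = 20.92 and enrolment unchanged is to keep K = 13.0 and label it as 95% power, two-sided 5%. The sponsor should confirm that this was the intention.
- Replace the loss row with a true statement: either that 25 allows up to 16% losses for N = 21, or that 20% losses from 25 leave 20 evaluable.
- Give the power at 20 evaluable for r = 0.692 as 94% by the Pearson/Fisher-z formula and about 88–93% for the planned Spearman test, with the variance factor (1.06 to 1 + r²/2) labelled as an assumption.
- If K = 7.85 with N = 14 (18 with losses) is mentioned at all, mark it as Pearson only.

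The cost is an edit to one table and a sentence of text. No additional participants are needed, and Section 2.6 can stay as it is.

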2.4 Selection criteria

2.4.1 Inclusion criteria

- Both genders
- Age 30 to 60 years
- BMI <25 kg/m²
- Patients who are not sedentary or who participate in heavy physical activities
- Stable weight in the last 3 months

2.4.2 Exclusion criteria

- Blood pressure >120/80 mmHg
- Glucose >100 mg/dL
- Glucose postprandial >140 mg/dL
- Cholesterol >200 mg/dL
- Triglycerides >150 mg/dL
- Smoking
- Women with polycystic ovary syndrome
- History of metabolic, cardiovascular, thyroid, renal, pancreatic and/or arterial hypertension disease
- Use of medications that modify insulin sensitivity (corticosteroids)
- Previous surgery or infection
- Symptoms of vomiting and/or excessive nausea

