2.4.3 Elimination criteria

- Nausea and/or vomiting
- Feeling faint or faint
- Intolerance to oral anhydrous glucose load
- Withdrawal of consent under information

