2.7.2 Laboratory determinations

For serum glucose measurements (fasting and PTOG at 3 h), secretion and sensitivity to insulin, total cholesterol, triglycerides, creatinine and uric acid, a catheter will be placed for the venous blood sample, the measurements will be made by simple enzymatic-colorimetric techniques with an automated clinical chemistry analysis equipment XL-100Erba® brand, which will be routinely calibrated according to the general laboratory log and will be operated by a single certified chemist assigned to this study.

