2.7.4 Description of the study

Scrutiny visit

All patients will be scheduled at 8:00 AM with a minimum of 8 hours of fasting. The candidate volunteers will be provided with the information regarding the study, and the benefits to their health, the possible adverse effects, the objectives and the methodology that will be implemented will be indicated, with the purpose of submitting to the patient's consideration the signature of the consent under information to accept to participate. Once signed, the screening tests will be carried out according to the inclusion criteria, as well as capturing the clinical history and the complete physical examination. A venous blood sample will be taken for evaluation of clinical biochemical selection criteria, which include serum concentrations of: fasting glucose, lipid profile, creatinine and uric acid.

All participants who satisfactorily meet the selection criteria will be included in the intervention phase..

Baseline visit (Day 1)

The patient will be scheduled at 8:00 AM with a minimum of 8 hours of fasting. Weight, height, waist circumference and blood pressure will be taken. Subsequently, a catheter will be placed for the venous blood sample; an oral glucose tolerance and insulin sensitivity test will be performed, for which a 75 g dose of glucose dissolved in water will be administered orally. After the ingestion of the glucose solution, the venous blood will be taken at times 0, 30, 60, 90, 120, 150 and 180 minutes.

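### Is the postprandial-glucose exclusion unworkable because screening describes only fasting bloods and no sampling time is given?

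*Combined protocol and SAP*

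**What the plan says.** Section 2.4.2 lists two glucose exclusions. "Glucose >100 mg/dL" can be checked on the fasting screening sample. "Glucose postprandial >140 mg/dL" cannot, because it needs a sample after a meal or a load, and the criterion names neither.

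Section 2.7.4 describes a fasted screening visit with one venous sample for "clinical biochemical selection criteria, which include serum concentrations of: fasting glucose, lipid profile, creatinine and uric acid". It continues: "All participants who satisfactorily meet the selection criteria will be included in the intervention phase". The 75 g load is given at the Day 1 visit, where "blood will be taken at times 0, 30, 60, 90, 120, 150 and 180 minutes". Section 2.7.2 refers to "serum glucose measurements (fasting and PTOG at 3 h" and adds no separate postprandial test.

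The elimination criteria in 2.4.3 include "Intolerance to oral anhydrous glucose load", with no glucose value attached. Section 3 does not mention participants whose Day 1 glucose is above the limit. Section 2.3 ends with a row labelled "n with 20 % losses", which gives 25.

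**The concern.** Read in sequence, the plan decides inclusion before it has the measurement that one exclusion criterion needs. Day 1 then yields six post-load values (30 to 180 minutes), and no sentence says which of them counts. A 30-minute value and a 120-minute value need not classify the same person alike. Nothing says whether someone over the limit on Day 1 is kept, dropped or replaced, or when that is decided.

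The analysis set is therefore partly open in a study of about 20 to 25 people. The glucose in question is also an input to what is being compared. By the formulas in 2.7.3, post-load glucose enters PREDIM, Cederholm, Avignon, Stumvoll and Gutt, and enters Matsuda through the mean. Section 1 classes Belfiore as based on the tolerance test. The other eight of the 14 comparators use fasting values only in their printed formulas. If the decision were taken after the indices were known, it could favour some correlations over others.

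**Working it through.** **Which sample is meant.** Section 1 describes the tolerance-test indices as taken over 120 minutes of a 75 g test. In 2.7.3 the only post-load glucose used at a single time is the 2-hour value (PREDIM, Cederholm, Avignon, Stumvoll, Gutt). The 3-hour label in 2.7.2 matches the length of the Day 1 sampling and is not shown to be a rival time for the criterion. The 120-minute value is the likely reading, though the plan does not say so.

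**The plan's own sample size.** Inputs from 2.3: r = 0.692, K = 13.0.
- C = 0.5 ln(1.692/0.308) = 0.8518
- n = 3 + 13.0/0.8518² = 20.92, as printed
- 20.92 × 1.2 = 25.1, the printed 25

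The allowance leaves 25 − 21 = 4 spare.

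**How many breaches.** The documents give no rate, so a range is assumed and breaches are treated as binomial among 25.

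| Assumed rate | Expected number | P(at least one) | P(more than 4) |
|---|---|---|---|
| 2% | 0.5 | 1 − 0.98²⁵ = 40% | below 0.1% |
| 5% | 1.25 | 1 − 0.95²⁵ = 72% | 0.7% |
| 10% | 2.5 | 1 − 0.90²⁵ = 93% | 9.8% |

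**What one participant does to Spearman's rho.** Start from rho = 0.692 at n = 24, an assumption borrowed from 2.3. Reverse the sign for indices that rise with insulin resistance. Since rho = 1 − Σd²/[n(n² − 1)/6] and 24 × 575/6 = 2300, Σd² = 0.308 × 2300 = 708.4. At n = 25 the divisor is 25 × 624/6 = 2600.
- Extreme on both indices: Σd² is unchanged, so rho = 1 − 708.4/2600 = 0.728 (+0.04).
- Extreme on PREDIM, mid-ranked on the comparator: in a simulation of 20,000 bivariate normal samples with population rho 0.692, mean rho falls from 0.669 to 0.628 (−0.04).
- At opposite extremes on the two indices: Σd² = 708.4 + 24 + 24² = 1308.4, so rho = 1 − 1308.4/2600 = 0.497.

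With two added participants (8,000 runs, starting from n = 23), the first two scenarios take mean rho from 0.665 to 0.739 or to 0.584.

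**Yardstick.** With the Bonett–Wright variance, the standard error of rho at n = 24 is about (1 − 0.692²) × √[(1 + 0.692²/2)/21] = 0.521 × 0.243 = 0.13. A shift of 0.04 is about a third of that.

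**Power if breaches are removed** (two-sided 0.05, r = 0.692). Take n = 18, that is 25 less 5 lost and 2 removed.
- Fisher z: 0.8518 × √15 = 3.30, power 91%.
- Bonett–Wright variance: 3.30/√(1 + 0.692²/2) = 2.96, power 84%.

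At n = 21 the two figures are 95% and 90%.

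**The case for a change.** The best case for a change is that the gap lies in the text itself and is cheap to close. A listed exclusion has no measurement behind it at the point of inclusion, no later rule deals with a breach, and a few sentences would remove a choice that could otherwise be made with the indices in view. The shifts of 0.04 are also scenarios, not limits: the fully discordant case reaches 0.497.

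Much of this is true as description. Screening lists no post-load test, even allowing that its list of bloods is not strictly exhaustive. The intolerance item in 2.4.3 does not settle the matter. It stands beside nausea and faintness and reads most naturally as tolerability. Yet those symptoms already have their own items and Section 1 uses glucose tolerance in the metabolic sense, so it may be meant to cover a high Day 1 value.

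Two parts do not stand. First, the plan does not license analysing someone over the limit: 2.4.2 excludes that person, 2.7.4 admits only those who meet the criteria, and keeping them would be a deviation. What is unstated is when the check is made, and Day 1 provides for it without a new test. Second, the discordant case needs one person to be the most resistant of 25 by PREDIM and the most sensitive by the comparator. That is implausible for indices meant to measure the same thing.

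**Conclusion.** No change to the plan follows. This is missing detail that an analyst would supply sensibly: judge the criterion on the Day 1 test, most likely at 120 minutes, from the glucose result and before the indices are calculated. Which sample counts, and whether a participant over the limit is removed or replaced, is for the sponsor to settle.

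The stakes are small. Between 0.5 and 2.5 participants of 25 are expected to be affected at assumed rates of 2% to 10%, and more than 4 is unlikely (at most about 10%). One such participant shifts a coefficient by about 0.04 in the two illustrative scenarios, in either direction. Power stays at 84% to 91% with 18 analysed. These figures rest on the assumed rates and on carrying r = 0.692 from 2.3 over to every comparator; the documents establish neither.
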